### 2.6.1 Will blood samples be obtained as part of this research study?

# \* No

\*If submitting a protocol for expedited review, it should be clear that the planned blood draws are within the parameters described here: http://www.hhs.gov/ohrp/policy/expedited98.html (see Expedited Research Category #2)

If **Yes**, address the frequency, volume per withdrawal, the total volume per visit, and the qualifications of the individual performing the procedure:

### **Study Flow Chart:**

Name	Modified Date
STUDY DIAGRAM - UPDATED 10-26-15.pdf	10/26/2015 11:13 AM

[reviewer notes¬]

2.7 Will follow-up procedures be performed specifically for research purposes? Follow-up procedures may include phone calls, interviews, biomedical tests or other monitoring procedures.

\* No

[reviewer notes¬]

2.8 Does this research study involve the use of any questionnaires, interview or survey instruments?

\* Yes

Upload a copy of all materials except for the SCID or KSADS which are on file at the IRB. The use of all instruments must be addressed in question 2.6 and/or question 2.7 (except for an exempt submission where they should be addressed on the appropriate uploaded exempt form).

Name	Modified Date
Primary Endpoint - PAC-SYM and FISI Questionnaires.pdf	11/3/2015 3:24 PM
SF-36 QUESTIONNAIRE in PDF.pdf	11/3/2015 3:24 PM
FIQL .pdf	11/3/2015 3:24 PM
PAC-QOL.pdf	11/3/2015 3:23 PM
Bowel Diary Pages.pdf	11/3/2015 3:35 PM

Previously the name and publisher for commercially available materials were listed in the textbox below but effective 9/1/2015, all materials (except for the SCID and KSADS) must be uploaded using the Add button above.

Each of these questionnaires (PAC-SYM, FISI, PAC-QOL, FIQL, SF-36) are open access.

[reviewer notes¬]

2.9 If subjects are also patients, will any clinical procedures that are being used for their conventional medical care also be used for research purposes?

\* yes

If **Yes,** describe the clinical procedures (and, if applicable, their frequency) that will be used for research purposes:

Anorectal function testing (anorectal sensory function and high resolution anorectal manometry [HRAM]) is commonly used for to help patients with anorectal dysfunction. The testing is typically performed once.

**2.10** The blood sample question was moved to 2.6.1.

[reviewer notes¬]

- 2.11 What is the total duration of the subject's participation in this research study across all visits, including follow-up surveillance?
  - Up to 8 weeks

[reviewer notes¬]

2.12 Does this research study involve any type of planned deception?

If Yes, you are required to request an alteration of the informed consent process (question 4.7)

\* No

[reviewer notes-]

- 2.13 Does this research study involve the use of UPMC/Pitt protected health information that will be de-identified by an IRB approved "honest broker" system?
  - \* No

[reviewer notes¬]

- 2.14 Will protected health information from a UPMC/Pitt HIPAA covered entity be accessed for research purposes or will research data be placed in the UPMC/Pitt medical record?
  - \* Yes

If you answer **Yes**, you are required to submit this study to the Research Informatics Office, Health Record Research Request (R3). Per UPMC Policy HS-RS0005, all research projects that access or involve UPMC electronic protected health information (e-PHI) must be submitted to R3, with the exception of clinical trials that are contracted through the UPMC Office of Sponsored Programs and Research Support (OSPARS).

Complete the R3 intake form available at http://rio.pitt.edu/services. An R3 representative will conduct a review. You will be notified once your R3 review is complete or if anything further is needed.

Describe the medical record information that will be collected from the UPMC/Pitt HIPAA covered entity and/or the research-derived information that will be placed in the medical records.

Basic Demographic information (age, sex, marital status, smoking and alcohol use, etc.)

MS-related information (duration of diagnosis, disease subtype, symptom assessment, current medication use)

Past medical history (particularly in regard to abdominal or anorectal surgeries, presence of inflammatory bowel disease, or recent infectious colitis)

- 2.14.1 Will protected health information from a non-UPMC/Pitt HIPAA covered entity be obtained for research purposes or will research data be placed in the non-UPMC/Pitt medical record?
  - \* No
  - I, [name], certify that any member of my research team accessing, reviewing and/or recording information from medical records have completed the CITI Privacy & Information Security course or, if completed within the past year, the Internet-Based Studies in Education and Research (ISER) HIPAA for Researchers (Formerly RPF Module 6). The HIPAA certificates must be available for review if audited but do not need to be uploaded into this OSIRIS application.
  - \* Yes
- 2.14.2 Are you requesting a waiver of the requirement to obtain written HIPAA authorization for the collection of the PHI?
  - \* No

[reviewer notes-]

- 2.15 Does this research study involve the long-term storage (banking) of biological specimens?
  - \* No

[reviewer notes¬]

- 2.16 Will research participants be asked to provide information about their family members or acquaintances?
  - \* No

[reviewer notes¬]

2.17 What are the main outcome variables that will be evaluated in this study?

PRIMARY END POINT: The primary end-point of the randomized clinical trial is a greater than 30% improvement in patients' subjective global assessment of bowel symptom severity after 4 weeks based on the answer to the following question: "Using a scale of 1 to 10 (1 being no problem and 10 being maximally impactful symptoms), how would you rate the severity of your bowel symptoms over the past 2 weeks?"

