# AIM 1: Determine the impact of timed rectal evacuation on anorectal dysfunction in MS patients

We will conduct a four week, single-center, randomized, double-blind placebo controlled clinical trial designed to assess the efficacy of timed rectal evacuation in improving the subjective global assessment of bowel symptoms in a cohort of patients with mild-to-moderate severity MS disease. Patients will be randomized 1:1 to administer either placebo or bisacodyl 10 mg rectal suppositories every other day during the 4 week trial. The primary endpoint will be the change in patients' rating of bowel symptom severity (10 point rating scale) at end of 4 weeks compared to baseline values. We will define an adequate treatment response as greater than a 30% reduction in symptom severity using an intention-to-treat analysis.

AIM 2: Determine the predictors of treatment response and impacts on quality of life

We plan to collect information on the patients' assessed severity of baseline and treatment-associated anorectal dysfunction, their impact on quality of life, as well as daily bowel diaries. Patients also will undergo anorectal sensory and manometric testing as a part of their routine clinical care. Enrolled patients that complete the study will be assessed for study medication compliance. All of these measures will be used to explore factors that are associated with treatment response. Changes in assessments of anorectal dysfunction-related quality of life will serve as key secondary end-points.

This proposal will significantly advance MS care and management by developing the evidence to support the adoption of a simple, safe, and cost-effective clinical treatment algorithm for anorectal dysfunction in the MS population. This paradigm for anorectal dysfunction management could be applicable to a majority of MS patients, and the treatment algorithm could be introduced to patients by nurses or mid-level clinical providers during points of routine MS patient care. Importantly, the treatment could be effectively accomplished by most patients and their caregivers at home. The findings of this investigation could also have a broader influence on care models for anorectal dysfunction associated with a range of other neurological illnesses, such as Parkinson's Disease, ALS, or stroke.

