#### SECONDARY END POINTS:

1) Daily Bowel Diaries – patients will record the consistency (Bristol Stool Scale, 1-7), number of bowel movements (BM), and occurrence of any fecal incontinence (FI) episodes each day. This data will be used to abstract BM and FI weekly frequency, as well as the mean change in stool consistency during the study period.

- 2) Patient Assessment of Constipation Symptom Questionnaire (PAC-SYM)
- 3) Fecal Incontinence Severity Index (FISI)
- 4) Patient Assessment of Constipation QOL (PAC-QOL)
- 5) Rockwood Fecal Incontinence Quality of Life Scale (FIQL)
- 6) SF-36 health status questionnaire
- 7) Study Medication Compliance
- 8) Anorectal Sensory and High Resolution Anorectal Manometry Testing: First sensation of rectal filling, urgency, and pain, basal anal resting pressure, voluntary anal squeeze pressure, and the rectal-anal inhibitory reflex (RAIR) to rectal distention and simulated strain, as well as the ability to evacuate a 50 cc volume rectal balloon within one minute.
- 2.18 Describe the statistical approaches that will be used to analyze the study data.
  - \* Addressed below:

Categorical data will be analyzed using Fisher's Exact tests for differences in proportions. Continuous data will be analyzed using Student's t-tests to detect differences in group means, with Bonferroni correction for multiple comparisons. We will use logistic regression to determine the factors that predict treatment responses.

A p<0.05 will be used as the threshold for statistical significance in all cases.

POWER ANALYSIS/SAMPLE SIZE: It is generally regarded that a 3-point reduction represents a clinically meaningful change using such a 10 point scale, and similar research studies using patient-reported outcomes have reported standard deviations ranging around ~2.5 points. However, we do not have baseline data to estimate variance, and thus we took a conservative estimate with an expected standard deviation of 4 points. Given these assumptions, we will need 28 patients in each study arm to detect at least a 30% reduction in symptom severity, with a power of 0.80, alpha=P<0.05 in a two-tailed analysis.

[reviewer notes-]

- 2.19 Will this research be conducted in (a) a foreign country and/or (b) at a site (e.g., Navajo Nation) where the cultural background of the subject population differs substantially from that of Pittsburgh and its surrounding communities?
  - \* No

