3.8 Does this research study involve neonates of uncertain viability or nonviable neonates?

\* No

[reviewer notes¬]

- 3.9 Fetal Tissues: Does this research involve the use of fetal tissues or organs?
  - \* No

[reviewer notes¬]
--->

3.10 What is the total number of subjects to be studied at this site, including subjects to be screened for eligibility?

Note: The number below is calculated by summing the data entered in question 3.11. Any additions or changes to the values entered in 3.11 will be reflected in 3.10.

- \* 400
- 3.11 Identify each of the disease or condition specific subgroups (include healthy volunteers, if applicable) that will be studied.

Click on the "Add" button and specify for each subgroup:

- 1) how many subjects will undergo research related procedures at this site; and
- 2) if applicable, how many subjects will be required to undergo screening procedures (e.g., blood work, EKG, x-rays, etc.) to establish eligibility. Do Not include subjects who will undergo preliminary telephone screening.

\*

Subgroup	Number to undergo research procedures	Number to undergo screening procedures
View MS patients	70	400

- 3.12 Provide a statistical justification for the total number of subjects to be enrolled into this research study at the multicenter sites or this site.
  - \* Described below:

The primary outcome measure is the group mean difference in subjective severity ratings of bowel symptoms using a 10 point scale. It is generally regarded that a 3-point reduction represents a clinically meaningful change using such a scale, and similar

Section: Section 3 - Human Subjects

research studies using patient-reported outcomes have reported standard deviations ranging around ~2.5 points on a 10 point scale. However, we do not have baseline data in this population to estimate variance, and thus we took a conservative estimate with an expected standard deviation of 4 points. Given these assumptions, we will need 28 patients in each study arm to detect at least a 3 point reduction in symptom severity, with a power of 0.80, alpha=P<0.05 in a two-tailed analysis.

Thus, the study is adequately powered if enrollment reaches 56 patients. However, to ensure adequate numbers in an intention-to-treat analysis, we will plan for a ~20% patient drop-out rate. Therefore, we will aim to enroll 70 patients in total.

[reviewer notes¬]

3.13 Inclusion Criteria: List the specific criteria for inclusion of potential subjects.

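### The plan names two primary endpoints, a more-than-30% improvement and a group mean difference, and its only power statement is for the mean

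*Combined protocol and SAP*

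**What the plan says.** All versions use the same single item, a 1-10 rating of bowel symptom severity, with the effect judged after 4 weeks. They differ in what is made of it.

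- **2.6 (Research plan) and 2.17 (Primary end point):** "The primary end-point of the randomized clinical trial is a greater than 30% improvement". This is a yes/no result for each patient.
- **3.12 (Justification of sample size):** "The primary outcome measure is the group mean difference in subjective severity ratings of bowel symptoms using a 10 point scale".
- **1.2, Aim 1:** the primary endpoint is the change in the rating from baseline to 4 weeks. The next sentence adds: "We will define an adequate treatment response as greater than a 30% reduction in symptom severity using an intention-to-treat analysis".
- **2.18 (Statistical approaches):** "Categorical data will be analyzed using Fisher's Exact tests for differences in proportions" and "Continuous data will be analyzed using Student's t-tests to detect differences in group means, with Bonferroni correction for multiple comparisons". It also sets p<0.05 as the threshold throughout. It ties neither test to the primary endpoint.
- **Sample size:** the assumptions are the same in both places, but 2.18 says "we will need 28 patients in each study arm to detect at least a 30% reduction in symptom severity" and 3.12 says "we will need 28 patients in each study arm to detect at least a 3 point reduction in symptom severity".
- **5.16 (Withdrawal):** a patient who withdraws after Phase 1 stays in the intention-to-treat analysis as a non-response.
- **2.6 (Phase 3):** after each patient's final questionnaires, the allocation is revealed to the patient and to the PI/Co-PI.

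**The concern.** A threshold response and a mean difference are different estimands with different tests, and they can lead to different conclusions from the same ratings. The plan has no rule for that case.

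The supporting parts are also split between the two. The mean has a power statement, but no rule for how a withdrawal enters a mean. The responder has a usable withdrawal rule and a named test, but no assumed response rates and no power. Section 5.12 expects some improvement in the placebo arm as well, so the placebo response rate cannot be taken as near zero.

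Because the PI/Co-PI learn each patient's arm as that patient finishes, a choice left open could be made with outcomes by arm in view. A reader of the result could not tell which power, which test level and which handling of withdrawals apply to the primary comparison.

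**Working it through.** **1. The plan's own figure.** Inputs from 2.18 and 3.12: difference 3 points, SD 4, two-sided 0.05, power 0.80, two equal arms.

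n per arm = 2 × ((1.96 + 0.842) × 4 / 3)² = 27.9, so 28. For drop-out, 56 / 0.8 = 70, or 35 per arm. Both figures reproduce. The noncentral t gives power 0.787 at 28 per arm with SD 4, and 0.993 with SD 2.5, the value the plan cites from similar studies. This is a calculation for two means; no response rate enters it.

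**2. Do a 30% reduction and a 3 point reduction agree?** As a share of a 10-point scale, 0.30 × 10 = 3, and they agree. As a percent of the patient's own baseline, 0.30 × baseline = 3 only when the baseline is 10. The plan does not state the denominator.

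**3. Power of the responder comparison with assumed rates.** The method is full enumeration of both binomials, rejecting when two-sided Fisher p<0.05. The active rate needed for 80% power is:

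| Assumed placebo rate | 28 per arm | 35 per arm |
|---|---|---|
| 20% | 58.9% | 54.0% |
| 30% | 70.4% | 66.2% |
| 40% | 79.1% | 75.3% |
| 50% | 86.5% | 83.2% |

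The differences are about 37-40 points at 28 per arm and 33-36 at 35 per arm. For 30% against 60%, power is 0.51 at 28 per arm and 0.62 at 35. For 30% against 70%, it is 0.79 and 0.88.

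**4. Rates derived from the plan's 3 points.** Assumptions: normal change, 30% read as percent of baseline, common baseline 5-9, placebo improvement 0-2. Three combinations that would put the active mean at or below 1 are left out, which leaves 12.

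Response probability = P(improvement > 0.3 × baseline). For example, with baseline 7, placebo improvement 0 and SD 4:
- placebo: 1 − Φ(2.1/4) = 0.300
- active: 1 − Φ((2.1 − 3)/4) = 0.589
- Fisher power at 28 per arm: 0.476

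Fisher power over the 12 combinations:

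| | SD 4 | SD 2.5 |
|---|---|---|
| 28 per arm, no withdrawals | about 0.48 | 0.86-0.89 |
| 35 per arm, 20% withdrawals as non-responders (rates × 0.8) | 0.34-0.44 | 0.67-0.85 |

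**5. Can the two analyses disagree?** Take a constructed case with 28 per arm, all at baseline 8. On placebo, 18 patients fall by 0 and 10 by 3; on active, 12 fall by 1 and 16 by 5. Under percent of baseline, a fall of 3 (37.5%) is a response, so responders are 10 against 16 and Fisher p=0.18, while the t-test gives p<0.001. This holds only under that reading. If a response needs a fall of more than 3 scale points, responders are 0 against 16 and both tests reject.

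**6. Cost of leaving the choice open.** In simulated null trials at 28 per arm (baseline 5-9, mean improvement 0-2, SD 2.5 or 4, percent of baseline), counting success if either test gives p<0.05 yields a false-positive rate of about 0.056-0.064 instead of 0.05. The range includes runs with ratings rounded and held within 1-10.

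**The case against.** The best defence is that 2.17 is the field for the primary endpoint and 2.6 repeats it. If it governs, 2.18 supplies Fisher's test and 5.16 supplies the withdrawal rule. Much of this stands: the test follows once the endpoint is fixed, and the responder's withdrawal rule is complete. So the documents do not support a reading that no test or withdrawal rule exists. But 3.12 states a different primary outcome just as plainly, and if 2.17 governs, the trial has no power statement for its primary endpoint.

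A second defence is that 3 points is 30% of a 10-point scale, so the two power sentences say the same thing. That is a fair reading, and under it the wording in 2.18 only needs clarifying. It does not turn a calculation for means into one for responders.

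A reader might also infer that the trial is underpowered. The documents do not show this. They give no response rates, and at SD 2.5 the illustrative completer power is above 0.80. The figure near 0.48 needs normally distributed change with SD 4, which fits a 1-10 item poorly. Nor is the sample-size arithmetic wrong, and the false-positive inflation is small.

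On the test level, 2.18 attaches Bonferroni to the t-tests and also applies p<0.05 throughout. That points towards 0.05 for the primary test but leaves doubt if the mean is primary.

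**Conclusion.** The concern holds in this form: current text names two primary endpoints, nothing chooses between them, and the stated power of 0.80 belongs to only one. For the responder endpoint in 2.17, the power is unstated and cannot be derived from the documents.

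The size can only be bracketed. With assumed placebo rates of 20-50%, 28 per arm gives 80% Fisher power only for differences of about 37-40 points. With rates derived from a 3-point effect, power ranges from 0.34 to 0.89 depending on the SD and on whether withdrawals are counted. The main weakness is the missing decision, made more serious by patient-by-patient unblinding of the PI/Co-PI; the modest rise in false positives is secondary. Once the endpoint is fixed, the test is settled. What remains is the denominator of the 30% and a matching power statement if the responder is chosen, or a withdrawal rule for the mean and a clear test level if the mean is chosen.

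**What to change.** Before outcomes by arm are seen, name one primary endpoint and its test in the same words in 1.2, 2.6, 2.17, 2.18 and 3.12, and make the other secondary. Either choice rests on text already in the plan.

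- **Responder primary.** State the denominator of the 30%, which is for the sponsor to choose. Use Fisher's test at two-sided 0.05, with withdrawals as non-responders. Replace the power statement in 2.18 and 3.12 with the assumed response rates among all randomised patients and the Fisher power they give at the planned 35 per arm. Enrolment need not change.
- **Mean change primary.** Express the effect in 2.18 as 3 points, as 3.12 does. State that the primary t-test is at two-sided 0.05, outside the Bonferroni correction. Add to 5.16 how withdrawals enter the mean analysis.

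The cost is wording in five sections, plus 5.16 under the second option, with no new measurements. One definition loses primary status. Under the first option the stated power may be less favourable than 0.80; if 30% against 60% were assumed, for example, it would be 0.62 at 35 per arm.

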#### SECONDARY END POINTS:

1) Daily Bowel Diaries – patients will record the consistency (Bristol Stool Scale, 1-7), number of bowel movements (BM), and occurrence of any fecal incontinence (FI) episodes each day. This data will be used to abstract BM and FI weekly frequency, as well as the mean change in stool consistency during the study period.

- 2) Patient Assessment of Constipation Symptom Questionnaire (PAC-SYM)
- 3) Fecal Incontinence Severity Index (FISI)
- 4) Patient Assessment of Constipation QOL (PAC-QOL)
- 5) Rockwood Fecal Incontinence Quality of Life Scale (FIQL)
- 6) SF-36 health status questionnaire
- 7) Study Medication Compliance
- 8) Anorectal Sensory and High Resolution Anorectal Manometry Testing: First sensation of rectal filling, urgency, and pain, basal anal resting pressure, voluntary anal squeeze pressure, and the rectal-anal inhibitory reflex (RAIR) to rectal distention and simulated strain, as well as the ability to evacuate a 50 cc volume rectal balloon within one minute.
- 2.18 Describe the statistical approaches that will be used to analyze the study data.
  - \* Addressed below:

Categorical data will be analyzed using Fisher's Exact tests for differences in proportions. Continuous data will be analyzed using Student's t-tests to detect differences in group means, with Bonferroni correction for multiple comparisons. We will use logistic regression to determine the factors that predict treatment responses.

A p<0.05 will be used as the threshold for statistical significance in all cases.

POWER ANALYSIS/SAMPLE SIZE: It is generally regarded that a 3-point reduction represents a clinically meaningful change using such a 10 point scale, and similar research studies using patient-reported outcomes have reported standard deviations ranging around ~2.5 points. However, we do not have baseline data to estimate variance, and thus we took a conservative estimate with an expected standard deviation of 4 points. Given these assumptions, we will need 28 patients in each study arm to detect at least a 30% reduction in symptom severity, with a power of 0.80, alpha=P<0.05 in a two-tailed analysis.

[reviewer notes-]

- 2.19 Will this research be conducted in (a) a foreign country and/or (b) at a site (e.g., Navajo Nation) where the cultural background of the subject population differs substantially from that of Pittsburgh and its surrounding communities?
  - \* No

Note that copies of training records, licenses, certificates should be maintained in the study regulatory binder and are subject to audit by the Research Conduct and Compliance Office (RCCO).

In addition, individuals planning to conduct human subject research outside the United States must complete an optional module on the CITI training website: International Studies. Click here to access the instruction sheet for accessing optional CITI modules.

[reviewer notes-]

Section: Section 3 - Human Subjects

[reviewer notes¬]

